8.1 Efficacy Assessments

8.1.1 Montgomery-Asberg Depression Rating Scale

The MADRS will be administered by a blinded and independent rater at the time points described in the schedule of assessments (Table 1.3-1). The baseline MADRS must be completed prior to or on the day of the baseline visit, or prior to usage of the digital therapeutic treatment following randomization. The MADRS at other visits may occur separately from the remote trial site visit but must be performed within the window.

The MADRS raters are selected, assigned, and managed by a central vendor separate from the trial sites.

Protocol No. 345-201-00002

The MADRS is the primary efficacy assessment of the subject's level of depression and must be administered utilizing the Structured Interview Guide for the MADRS (SIGMA). The MADRS consists of 10 items, each rated from 0 to 6. A higher score on the MADRS represents a higher severity of the level of depression.

8.1.2 Generalized Anxiety Disorder-7

The GAD-7 will be self-reported by the subject electronically within the window of the remote visits described in the schedule of assessments (Table 1.3-1). It is recommended that the GAD-7 be completed prior to the remote visit.

The GAD-7 is designed to assess anxiety in subjects. The scale contains 7 items and each item is rated from 0 (not at all) to 3 (nearly every day). The score ranges from 0 to 21. A higher score on the GAD-7 represents greater anxiety symptomatology.

8.1.3 Clinical Global Impressions-Severity

The CGI-S will be administered by trial site staff at the time points described in the schedule of assessments (Table 1.3-1).

The CGI-S is a standardized, clinician-administered global rating scale that measures disease severity on a 7-point Likert scale. A higher score on the CGI-S represents a higher severity of disease.

8.1.4 Patient Health Questionnaire-9

The PHQ-9 will be self-reported by the subject electronically within the window of the visits at the time points described in the schedule of assessments (Table 1.3-1). It is recommended that the PHQ-9 be completed prior to the visit.

The PHQ-9 is a standardized, self-administered rating scale that assesses the severity of depressive symptoms. The scale consists of 9 items, representing the 9 criteria upon which the diagnosis of DSM-IV depressive disorders is based. A higher score on the PHQ-9 represents a higher severity of depressive symptoms.

8.1.5 World Health Organization Disability Assessment Schedule 2.0

The WHODAS 2.0 will be self-reported by the subject electronically within the window of the remote visits at the time points described in the schedule of assessments (Table 1.3-1). It is recommended that the WHODAS 2.0 be completed prior to the remote visit.

The WHODAS 2.0 is a 36-item self-assessment scale to measure a subject's function and disability across 6 domains of life: cognition (understanding and communicating), mobility (moving and getting around), self-care (hygiene, dressing, eating, staying alone),

Protocol No. 345-201-00002

getting along (interacting with others), life activities (domestic responsibilities, leisure, work and school), and participation (community and society).

8.2 Safety Assessments

Details pertaining to the definitions, collection, reporting, and follow-up of AEs are described in Section 8.3.

8.2.1 Clinical Laboratory Assessments

A urine drugs-of-abuse screen and pregnancy testing will be performed as described in Section 8.4.7 and Section 10.3, respectively.

Other clinical laboratory testing is not planned, but the investigator may perform tests as needed to ensure subject safety. The medical monitor should be consulted prior to clinical laboratory testing.

8.2.2 Suicidality Monitoring

Suicidality monitoring will occur at the time points described in the schedule of assessments (Table 1.3-1).

In the event of clinically important treatment emergent suicidal ideation or suicidal behavior, as per the investigator's judgment, the subject may be withdrawn from the trial and may receive appropriate medical care, which may include increasing the dose of ADT or using other medications as per the standard of care treatment for depression and/or access to a suicide hotline. The investigator will follow-up until the subject's condition has stabilized.

Protocol No. 345-201-00002

Clinically important suicidality may include but is not limited to:

- Suicidal behavior (with or without intent of suicide or serious self-harm).
- Acute suicidality to such a degree that precaution against suicide must be exercised.
- Response of "yes" to C-SSRS ideation items 4 or 5 or any of the C-SSRS behavioral items.
- Score of "4", "5", or "6" on the MADRS suicidal thoughts item.

8.2.2.1 Columbia-Suicide Severity Rating Scale

The C-SSRS will be administered by trial site staff at the time points described in the schedule of assessments (Table 1.3-1).

The C-SSRS is an assessment tool that evaluates suicidal ideation and behavior. The "Baseline/Screening" Version will be used for the first administration (at the screening visit). This version will evaluate a lifetime assessment of suicidal ideations and behaviors, as well a past 12-month evaluation of suicidal ideations and a past 24-month evaluation of suicidal behaviors. Subsequent visits will utilize the "Since Last Visit" Version.

8.3 Adverse Events

8.3.1 Definitions

Note: The below definitions of AE, SAE, device-related AE, and unanticipated adverse device effect (UADE) are based on ISO14155 and 21 CFR 812 (and related US Food and Drug Administration [FDA] medical device clinical trial guidance documents).

Adverse event: Any untoward medical occurrence, unintended disease or injury, or untoward clinical sign in subjects, whether or not related to the digital therapeutic. Including any newly occurring event or previous condition that increases in severity or frequency following enrollment in the trial.

Note: Adverse events would not include information recorded as medical history at screening for preplanned procedures for which the underlying condition was known and no worsening occurred.

Serious AE: An AE where the outcome is one of the following:

- a) Led to death
- b) Led to a serious deterioration in the health of the subject, that either resulted in
 - 1) A life-threatening illness or injury, or
 - 2) A permanent impairment of a body structure or a body function, or
 - 3) In-patient hospitalization or prolongation of existing hospitalization, or

Protocol No. 345-201-00002

- 4) A medical or surgical intervention to prevent permanent life-threatening illness or injury or permanent impairment to body structure or a body function.
- c) Led to fetal distress, fetal death, or a congenital abnormality
- d) Other medically significant events that, based upon appropriate medical judgment, may jeopardize the subject and may require medical or surgical intervention to prevent one of the outcomes listed above; eg, worsening of depression or anxiety symptoms; disease progression; suicidality (ideation); develop or resume drug dependency or drug abuse.

Note:

- Hospitalization itself should not be reported as an SAE; whenever possible the reason for the hospitalization should be reported.
- Hospitalizations or prolonged hospitalizations for social admissions (ie, those required for reasons of convenience or other nonmedical need) are not considered SAEs.
- Prescheduled hospitalization to address a condition that has existed prior to the signing of the ICF should not be considered an SAE.

Device-related AE: Events directly attributable to the device itself.

Unanticipated adverse device effect: Any serious adverse effect on health or safety or any life-threatening problem or death caused by, or associated with, a device, if that effect, problem, or death was not previously identified in nature, severity, or degree of incidence in the investigational plan, or any other unanticipated serious problem associated with a device that relates to the rights, safety, or welfare of subjects.

Nonserious AEs: All AEs that do not meet the criteria for a "serious" AE.

Severity: Adverse events will be graded on a 3-point scale and reported as indicated in the eSource. The severity of an adverse experience is defined as follows:

1 = Mild: Discomfort noticed, but no disruption to daily activity.

2 = Moderate: Discomfort sufficient to reduce or affect normal daily activity.

3 = Severe: Inability to work or perform normal daily activity.

Causality: Assessment of causal relationship of an AE to the use of CT-152 is defined as follows:

Related: There is a reasonable possibility of a temporal and causal

relationship between CT-152 and the AE.

Not Related: There is no temporal or causal relationship between CT-152 and

the AE.

Additional definitions (based on Otsuka internal procedures):

63

Protocol No. 345-201-00002

Treatment-emergent AEs (TEAEs): TEAEs are defined as an AE that began after at least one occurrence of CT-152 or sham; or if the event was continuous from baseline and was worsening, serious, related, or resulted in death, discontinuation, or interruption of investigational product.

8.3.2 Eliciting and Reporting Adverse Events

The investigator will regularly assess subjects for the occurrence of AEs. To avoid bias in eliciting AEs, subjects should be asked the nonleading question: "How have you felt since your last visit?" All AEs (serious and nonserious) reported by the subject must be recorded on the source documents provided by the sponsor and in eSource. Adverse event collection will begin after a subject signs the ICF through the last visit or contact.

Medical terminology should be used for AE reporting. Adverse events should be reported as a single unifying diagnosis whenever possible or, in the absence of a unifying diagnosis, as individual signs or symptoms. Exacerbation or disease progression should be reported as an AE only if there are unusual or severe clinical features that were not present, or experienced earlier, or not expected based on the course of the condition.

A reported AE that undergoes a change in severity, seriousness, or toxicity should be reported as a new AE on the source documents and on the eSource provided by the sponsor.

Adverse event, start date, end date, seriousness, severity, relationship to trial treatment (causality), action taken with trial treatment and outcome will be recorded on the source documents and in eSource.

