If a subject contacts the call center with a possible or suspected product quality complaint (PQC), the call center will log the call. All call records (tickets) captured by the call center will be provided to the Click Therapeutics Quality Team for PQC analysis, tracking, and resolution.

If a subject reports a possible or suspected PQC to the investigator or designee during a remote visit or telephone contact, the investigator or designee is to immediately contact the call center, which will log the call and immediately provide the information to the Click Therapeutics Quality Team.

In addition to call tracking, calls with the call center may be recorded for quality purposes. Call center contact information and processes are detailed in the Site Operations Manual.

Trial Assessments:

Assessments for Efficacy: MADRS, GAD-7, CGI-S, WHODAS 2.0, and PHQ-9.

Assessments for Safety: AEs (including AEs related to the worsening of depressive symptoms) and C-SSRS.

Screening/Other: M.I.N.I, HAM-D₁₇, Antidepressant Treatment Response Questionnaire, *DSM-5* diagnosis of MDD, urine drugs-of-abuse screen, pregnancy test, and adherence check.

Data Monitoring Committee:

A Data Monitoring Committee (DMC) will be chartered for this trial. The DMC will include at least 3 members, one of whom will be an expert in biostatistics for clinical trials, and at least one of which will have expertise in MDD treatment trials. The DMC will be convened at intervals described in the DMC charter to review data on recruitment, retention, interim analysis, and safety (including evaluation of discontinuation criteria), and to review data for completeness and quality during the trial. Discontinuation criteria will be prespecified and included in the DMC charter.

Statistical Methods:

The initial sample size is calculated to detect a 3-unit difference between CT-152+ADT and sham+ADT in the change from baseline in MADRS total score with 85% power at a 2-sided $\alpha = 0.05$ level, assuming a common standard deviation of 9. The resulting sample size is 324 evaluable subjects in total (162 subjects in each arm). To compensate for subjects that fail to have evaluable assessments of MADRS total score in the full analysis set (FAS) sample (estimated at up to 10% of all subjects), a total of 360 subjects (180 subjects in each arm) will be randomized in this trial.

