8.3.2.1 Anticipated Adverse Events

Adverse events related to mobile device use may include dizziness, fatigue, or headache. No attributable AEs to CT-152 were observed in previous research studying CT-152. Please refer to the CT-152 Investigator Brochure for additional risk information.

Subjects enrolling in this trial will have a diagnosis of MDD per *DSM-5* criteria. Any worsening of the symptoms associated with MDD, as well as other relevant comorbidities for this population including anxiety disorder or new or relapse to substance use are anticipated AEs for this population.

Efficacy assessments and safety variables per Section 8.1 and Section 8.2 captures measurement criteria for some of these anticipated AEs. Subjects are under the care of qualified HCPs during the trial, and will be assessed for all AEs (anticipated as noted here) and unanticipated.

Protocol No. 345-201-00002

The risk profile of ADTs used as standard of care in clinical practice is well understood and is detailed in the package insert of the medications. Based on the known risk profile of the ADT medications and preliminary risk assessment of CT-152, the sponsor believes, that there is no additional risks to the subjects.

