9.4.2.3 Other Safety Data

Rates of the incidence of worsening depressive symptoms during the treatment period (depressive symptom severity entering the "severe" range: CGI-S increase of 2 or more points from baseline, or as judged by investigator evaluation) and the incidence of emergent clinically important suicidality (as described in Section 8.2.2) will be compared between CT-152 and sham groups in the safety analysis sets. Rates and their 95% confidence intervals will be reported and the estimated differences between groups will be provided.

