# 9.4 Other Safety Analysis

The incidence of worsening depressive symptoms during the treatment period will be compared between CT-152 and sham groups using Cochran-Mantel-Haenszel (CMH) General Association Test on OC dataset. Worsening depressive symptoms are defined as 1) CC 2) Any AE of worsening depression. Rates and

their 95% confidence intervals will be reported and the estimated differences between groups will be provided.

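### Protocol 8.3.2 conflicts with 8.3.1 and 8.3.2.1 on whether worsening depression is an adverse event, and SAP 9.4 counts those events, so recording may be incomplete and differ by site

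*Protocol*

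**What the plan says.** Four places in the protocol bear on whether worsening depression is recorded as an AE.

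- **8.3.2 (reporting instruction):** "Exacerbation or disease progression should be reported as an AE only if there are unusual or severe clinical features that were not present". The sentence goes on to add features experienced earlier or not expected from the course of the condition.
- **8.3.1 (definition of an AE):** "Including any newly occurring event or previous condition that increases in severity or frequency following enrollment in the trial". The same section gives worsening of depression and disease progression as examples of medically significant serious events.
- **8.3.2.1 (anticipated events):** "Any worsening of the symptoms associated with MDD, as well as other relevant comorbidities for this population" are named as anticipated AEs in this population.
- **1.1 Synopsis (safety assessments):** "AEs (including AEs related to the worsening of depressive symptoms) and C-SSRS".

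The outcome that uses these records is defined twice. Protocol 9.4.2.3 describes worsening into the severe range as "CGI-S increase of 2 or more points from baseline, or as judged by investigator evaluation", and does not name AE records. SAP 9.4 gives two components. The first is blacked out in the public copy, and the second is "Any AE of worsening depression". The SAP compares the arms with a Cochran-Mantel-Haenszel test and reports rates, 95% confidence intervals and differences.

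**The concern.** A site that follows 8.3.2 as written leaves out ordinary worsening of depression. A site that follows 8.3.1 and 8.3.2.1 records it. The word anticipated in 8.3.2.1 sharpens the clash: a site can read it as a statement that worsening is expected, and so as grounds for leaving it out under 8.3.2. Neither site has made an error, because the protocol does not rank the two rules.

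The difference reaches a prespecified comparison. The second SAP component can count only what sites have entered as AEs, and the general tables of treatment-emergent AEs draw on the same records. Events not entered during the trial cannot be recovered reliably afterwards. At stake is whether the reported rates of worsening depression, and the difference between arms, mean the same thing at every site.

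**Working it through.** **Step 1: the rules side by side.** Take a participant whose depression worsens moderately, with no unusual, severe or unexpected features.

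| Source | Is this recorded as an AE? |
|---|---|
| Protocol 8.3.1, AE definition | Yes: a previous condition that increased in severity |
| Protocol 8.3.2 | No: none of the qualifying features |
| Protocol 8.3.2.1 | Yes: worsening MDD symptoms are an anticipated AE |
| Protocol synopsis | Yes: listed among the safety assessments |

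The SAP's second component counts this participant only if the site answered yes.

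**Step 2: what else could catch the event.** By the Schedule of Assessments, CGI-S is rated at baseline and at Weeks 2, 4 and 6. A rise of 2 or more points found there does not depend on AE reporting. A one-point rise, or worsening that resolves between ratings, would be missed by that criterion. AEs are also collected at the Week 1, 3 and 5 telephone contacts. The protocol's investigator-evaluation route is not tied by its wording to AE records. The SAP's first component cannot be read, so its overlap with the second cannot be checked.

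**Step 3: size, as an illustration.** The documents give no expected rate and no figure to reproduce for this outcome. Inputs:

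- n = 180 per arm (Protocol 9.1, initial sample size).
- True rates of 8% and 16% (assumed).
- f, the share of worsening events found only through AE reports: 0.25, 0.5 or 0.75 (assumed).
- c, the share of those that sites record: 0.75, 0.5 or 0.25, the same in both arms (assumed).

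Only AE-only events can be lost, so each observed rate is the true rate times k = (1 − f) + f × c.

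Power for two proportions at two-sided 0.05 is Φ[(d − 1.96 × SE0) / SE1]. Here d is the difference in observed rates, SE0 uses the pooled rate, and SE1 uses the separate rates.

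Full capture (k = 1): d = 0.08; SE0 = √(0.12 × 0.88 × 2/180) = 0.03425; SE1 = √((0.08 × 0.92 + 0.16 × 0.84)/180) = 0.03399. Power = Φ[(0.08 − 0.06714)/0.03399] = Φ(0.378) = 65%.

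Worst cell (f = 0.75, c = 0.25): k = 0.25 + 0.1875 = 0.4375, so the rates are 3.5% and 7.0% and d = 0.035. SE0 = √(0.0525 × 0.9475 × 2/180) = 0.02351; SE1 = √((0.035 × 0.965 + 0.07 × 0.93)/180) = 0.02344. Power = Φ[(0.035 − 0.04608)/0.02344] = Φ(−0.473) = 32%.

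| f | c = 0.75 | c = 0.5 | c = 0.25 |
|---|---|---|---|
| 0.25 | 62% | 58% | 55% |
| 0.5 | 58% | 51% | 44% |
| 0.75 | 55% | 44% | 32% |

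Across the table k runs from 0.4375 to 0.9375. Observed rates run from 3.5% vs 7.0% to 7.5% vs 15.0%, and the risk difference from 3.5 to 7.5 points against a true 8. The risk ratio is 2 in every cell, because k multiplies both arms.

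With lower assumed true rates of 5% and 10%, full capture gives 44%. Over f from 0.25 to 0.75 and c from 0.25 to 0.5, power is 21% to 39%.

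**The case against.** A reader might infer that worsening depression will be under-recorded. The documents do not support that. Sections 8.3.1 and 8.3.2.1 and the synopsis tell sites to treat it as an AE, the treatment-emergent definition in 8.3.1 includes events continuing from baseline that worsen, and 8.3.2 still admits unusual or severe worsening. Contradictory instructions make loss possible, not certain, and its size cannot be derived from the plan.

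A reader might also apply the loss to the whole outcome. At 8% and 16% that gives power of 51%, 36% and 20% with 75%, 50% and 25% of events recorded. It would require every event to be found only through AE reports, whereas the SAP has two components and the protocol's CGI-S route is independent of AE entry.

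A third tempting step is to say that site variation biases the comparison between arms. Randomization is stratified by site, so site habits should fall on both arms alike, and equal loss leaves the risk ratio intact. That stands, with one limit. Protocol 4.2 and 6.3 accept that site staff may become unblinded. The central blinded rater protects MADRS, not AE entry, so equal capture is not guaranteed.

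Finally, the importance should not be inflated. The listed safety endpoint is the frequency and severity of AEs, serious AEs and discontinuations due to AEs. Worsening depression sits under other safety analyses, and the trial is sized on MADRS, so power is only a rough yardstick here. MADRS and C-SSRS to Week 10 and CGI-S to Week 6 measure deterioration independently. These points limit the consequence. They do not remove the conflict between the reporting rules.

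**Conclusion.** The point holds as an internal inconsistency. Section 8.3.2 excludes ordinary worsening that 8.3.1 and 8.3.2.1 include, SAP 9.4 counts such events, and nothing reconciles them. Recording may be incomplete and may differ across about 50 sites. With equal capture, the observed rates, risk difference and power fall and the risk ratio does not change. In the illustration, power drops from 65% to between 32% and 62%. That range rests on the assumed rates of 8% and 16%, 180 per arm, the assumed f and c, and equal capture in both arms. It shows how the mechanism works and is not a forecast. The outcome's second component also differs between the documents: investigator evaluation in Protocol 9.4.2.3, an AE record in SAP 9.4.

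**What to change.** Reconcile Protocol 8.3.1, 8.3.2 and 8.3.2.1 into one AE-recording rule for worsening of depressive symptoms that matches what SAP 9.4 counts. One way is a sentence in 8.3.2 stating that its restriction on exacerbation does not apply to worsening of depressive symptoms. Then give the second component of the outcome a single definition in Protocol 9.4.2.3 and SAP 9.4, saying whether investigator evaluation means an AE record or a separate judgement and, if separate, where it is captured.

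This changes recording and definitions only, not how any participant is managed. The cost is a short text change in each document, a site training note and somewhat more AE records. It should be done before or during conduct, since unrecorded events cannot be reliably recovered later.

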8.3.2.1 Anticipated Adverse Events

Adverse events related to mobile device use may include dizziness, fatigue, or headache. No attributable AEs to CT-152 were observed in previous research studying CT-152. Please refer to the CT-152 Investigator Brochure for additional risk information.

Subjects enrolling in this trial will have a diagnosis of MDD per *DSM-5* criteria. Any worsening of the symptoms associated with MDD, as well as other relevant comorbidities for this population including anxiety disorder or new or relapse to substance use are anticipated AEs for this population.

Efficacy assessments and safety variables per Section 8.1 and Section 8.2 captures measurement criteria for some of these anticipated AEs. Subjects are under the care of qualified HCPs during the trial, and will be assessed for all AEs (anticipated as noted here) and unanticipated.

Protocol No. 345-201-00002

The risk profile of ADTs used as standard of care in clinical practice is well understood and is detailed in the package insert of the medications. Based on the known risk profile of the ADT medications and preliminary risk assessment of CT-152, the sponsor believes, that there is no additional risks to the subjects.

